Title:

Lemborexant Augmentation of Naltrexone for Alcohol Craving and Sleep: A Randomized, Double-Blind, Placebo- Controlled Study

NCT number: NCT05458609

Date: 08/01/2024

Background

Alcohol is one of the most popular substances used worldwide for thousands of years. Globally, harmful alcohol use continues to be a major public health and economic burden. The World Health Organization global status report attributed harmful alcohol use to 3 million deaths in 2016. (*Global Status Report on Alcohol and Health 2018*, n.d.) In the United States, alcohol is the most used substance by people over the age of 12, with alcohol use disorder (AUD) affecting 14.5 million people in this age group. Hazardous alcohol use is associated with emergency room visits, overdose, driving fatalities and chronic medical conditions such as liver disease, heart disease, and hypertension. (*Alcohol Facts and Statistics | National Institute on Alcohol Abuse and Alcoholism (NIAAA)*, n.d.)

Pharmacological interventions for AUD have expanded over the past few decades, including FDA approved and off-label medications such as naltrexone that have demonstrated efficacy in reducing alcohol cravings, consumption, and likelihood of relapse. (Swift & Aston, 2015; Zindel & Kranzler, 2014) However, the significant variability in response to treatment fuels ongoing interest in novel pharmacotherapy for AUD. A common approach involves repurposing readily available medications based on our understanding of AUD pathophysiology. In this study, we focus on the orexin system, which has been implicated in behaviors such as feeding, sleep-wake cycle, motivation, and reward associated with food, sex and substances including alcohol. (Li et al., 2016) The brain neuropeptides orexin A and orexin B originate in the hypothalamus and project throughout the central nervous system, activating G-protein-coupled receptors orexin 1 and 2 (OX1R and OX2R). While both orexin receptors are involved in addictive behaviors, OX1R signaling has a stronger association with reward processes whereas OX2R promotes arousal. Chronic alcohol exposure may lead to neuroadaptations in the orexin system, as observed in studies showing a positive correlation between orexin levels and severity of alcohol dependence and distress during alcohol withdrawal. (Goltz et al., 2009; Ziółkowski et al., 2016) Moreover, multiple animal studies have demonstrated efficacy of orexin antagonists in reducing alcohol craving, self-administration, and reinstatement of alcohol use induced by cues and stress. (Moorman, 2018)

The orexin antagonist lemborexant is FDA approved for treatment of insomnia. Lemborexant acts on both OX1R and OX2R and has shown efficacy in sleep initiation and maintenance compared to placebo on polysomnography and patient-report.(Rosenberg et al., 2019) It has demonstrated long-term safety and effectiveness without physical dependence or rebound insomnia.(Murphy et al., 2017; Yardley et al., 2021) Compared to suvorexant, another orexin antagonist, lemborexant has greater selectivity and stronger binding for orexin receptors. Suvorexant has secondary effects on the adenosine receptor and dopamine transporter whereas lemborexant only has weak binding to melatonin 1. These differences may increase risk of misuse for suvorexant more than lemborexant.(Asakura et al., 2021) In addition, Lemborexant's longer half-life (17-19h) may be advantageous for reduction of cravings during the day.(Landry et al., 2021)

In people with AUD, insomnia is a common problem that is associated with alcohol craving and relapse.(He et al., 2019) Standard treatment for AUD with naltrexone improves cravings and other AUD outcomes, but does not improve sleep. In some cases, naltrexone may have a detrimental effect on sleep.(Anton et al., 2006; Panin & Peana, 2019) Lemborexant may be able to target both alcohol craving/urges and insomnia when added to standard treatment with naltrexone.

Aims and hypothesis

Our primary goal is to evaluate the effects of naltrexone plus lemborexant augmentation compared to naltrexone plus placebo on cue-induced and non-cued alcohol craving scores. Our secondary goals are to evaluate the effects of this combination on sleep quality using actigraph data.

Hypotheses: H1: we hypothesize that the group receiving naltrexone plus lemborexant augmentation will have a greater decrease in cue-induced and non-cued alcohol craving scores than naltrexone plus placebo. H2: we hypothesize that the group receiving naltrexone combined with lemborexant will experience a greater improvement on objective sleep measures.

Significance of the problem

Alcohol use disorder (AUD) and insomnia are highly comorbid in our psychiatric inpatients. In people with AUD, insomnia may be persistent and is associated with alcohol craving and relapse. Standard treatment for AUD with naltrexone improves cravings and other AUD outcomes, but does not improve sleep. In some cases, naltrexone may have a detrimental effect on sleep. Insomnia is associated with higher severity of depression, anxiety, and suicidality. Adequate treatment of both alcohol cravings and insomnia may improve overall outcomes.

Design and methods

The study will be a randomized, double-blind, placebo-controlled clinical trial of naltrexone plus placebo versus naltrexone plus lemborexant conducted at The Menninger Clinic on inpatients with alcohol use disorder. Recruitment will occur on patients admitted to a Menninger inpatient unit over a 12-month period. Because the average length of stay at The Menninger Clinic is 2 to 4 weeks, the study period will last 2 to 4 weeks depending on the patient's length of stay. We plan to enroll 10 patients and randomize half to lemborexant plus naltrexone and half to placebo plus naltrexone using a computer-generated randomization scheme.

All participants will receive a standard treatment program with pharmacotherapy for their psychiatric conditions, CBT, DBT, individual therapy, and group therapy during their inpatient admission. Subjects will be randomly assigned to either naltrexone plus placebo or naltrexone plus lemborexant. For all patients, naltrexone will be given at 50 mg/day. For the lemborexant augmentation group, lemborexant will be given at 10mg at bedtime. Dose reductions due to tolerability will be permitted at the discretion of the investigator. Blinding will be ensured by use of a matching placebo for lemborexant 10mg using over-encapsulation. Participants and study personnel will be blinded to the study drug. Medications will be administered by nursing staff. All participants will be exposed to alcohol-related cues using virtual reality technology at baseline, at the end of week 2 or end of week 4.

Safety: Safety assessments will be collected weekly throughout the study. These assessments will consist of monitoring and recording of adverse events and periodic measurement of vital signs.

Assessment and Outcomes Measures (Tables 1 and 2): As part of the Menninger Clinic inpatient evaluation, each patient will be given a medical examination, including physical exam and laboratory testing on admission. Assessments will include baseline EKG, CBC, BMP, liver profile, pregnancy test (females), and urine drug screen. This information is part of the health record and will be collected for screening and analysis.

Clinical diagnoses including alcohol use disorder will be assessed using the structured clinical interview for DSM-5 (SCID-5). Alcohol use disorder severity will be measured using the alcohol dependence scale (ADS). We will also be using an actigraph to measure total sleep time and wake after sleep onset. Cue-induced alcohol cravings will be assessed using the Alcohol Urge Questionnaire (AUQ) and non-cued alcohol craving will be assessed using the Penn Alcohol Craving Scale (PACS).

Table 1: Initial Assessment, Sleep, Mood, and Suicide risk

Measure	Instrument	Screening	Daily	Weekly	Discharge
DSM-5 Diagnoses (including Alcohol use disorder)	Structured Interview for DSM-5 (SCID-5)	X			
Alcohol Use Disorder Severity	Alcohol Dependence Scale (ADS)	X			
Total Sleep Time, wake after sleep onset	ActiGraph wGT3X-BT	X		X	X

Table 2: Alcohol Craving Measures

Measure	Instrument	Baseline	Week 1	Week 2	Week 3	Week 4
Cue-induced alcohol craving	Alcohol Urge Questionnaire (AUQ)	X	x	x	x	x
Non-cued alcohol Craving	Penn Alcohol Craving Scale (PACS)	X	X	X	X	X

Statistical Analysis: Descriptive statistics and bivariate tests will be used to inspect distributional properties of sample demographics and clinical outcomes at baseline, within the sample and between participant subgroups (e.g., gender, age, AUD severity). All outcome measures and safety assessments will be summarized weekly over the study period. Additionally, variables that significantly differ between participants who dropped out of the study and those who did not will be controlled statistically in our hypothesis testing to minimize any systematic bias due to attrition. Hierarchical linear modeling (HLM) will be conducted to examine the effects of receiving naltrexone plus lemborexant augmentation versus naltrexone plus placebo, while properly accounting for (a) the dependency of observations—i.e., correlation of repeated measurements (level 1) within participants (level 2) and (b) any difference due to receiving the treatments in a different group. Appropriate covariance structures will be determined in a preliminary analysis (i.e., intercept-only model) based on model fit (e.g., adjusted Akaike Information Criterion, Bayesian Information Criterion). Statistical significance will be determined at 0.05 alpha level.

Sample Size and Power: The study is a pilot trial with a purpose of obtaining *unbiased* effect sizes for naltrexone plus lemborexant augmentation prescribed to a small number of adult patients with AUD. No formal power calculation is

applicable because this is a first-in-human study and relevant data is not available in the literature.

References

Alcohol Facts and Statistics / National Institute on Alcohol Abuse and Alcoholism

(NIAAA). (n.d.). Retrieved October 14, 2021, from

<https://www.niaaa.nih.gov/publications/brochures-and-factsheets/alcohol-facts-and-statistics>

Anton, R. F., O'Malley, S. S., Ciraulo, D. A., Cisler, R. A., Couper, D., Donovan, D.

M., Gastfriend, D. R., Hosking, J. D., Johnson, B. A., LoCastro, J. S.,

Longabaugh, R., Mason, B. J., Mattson, M. E., Miller, W. R., Pettinati, H. M.,

Randall, C. L., Swift, R., Weiss, R. D., Williams, L. D., ... COMBINE Study

Research Group, for the. (2006). Combined Pharmacotherapies and

Behavioral Interventions for Alcohol DependenceThe COMBINE Study: A

Randomized Controlled Trial. *JAMA*, 295(17), 2003–2017.

<https://doi.org/10.1001/jama.295.17.2003>

Asakura, S., Shiotani, M., Gauvin, D. V., Fujiwara, A., Ueno, T., Bower, N.,

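### The AUQ is scheduled weekly as the cue-induced craving measure, but cue sessions are described only at baseline and at week 2 or week 4, and the analysis does not separate cued from uncued scores

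*Combined protocol and SAP*

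**What the plan says.** The primary goal (Aims and hypothesis) is to compare the arms "on cue-induced and non-cued alcohol craving scores". H1 names both kinds of craving, and neither is ranked first.

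Assessment and Outcomes Measures assigns the AUQ to cue-induced craving and the PACS to non-cued craving. In "Table 2: Alcohol Craving Measures" the AUQ row carries the cue-induced label and is marked at all five time points: "Alcohol Urge Questionnaire (AUQ) X x x x x".

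Design and methods describes the cue sessions. All participants are to be "exposed to alcohol-related cues using virtual reality technology at baseline, at the end of week 2 or end of week 4". The same section says that "the study period will last 2 to 4 weeks depending on the patient's length of stay".

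Statistical Analysis specifies hierarchical linear modelling of repeated measurements nested within participants, and adds that "All outcome measures and safety assessments will be summarized weekly over the study period". It does not list the AUQ visits that enter the model and has no term for whether a score followed a cue. Nowhere do the documents say whether the AUQ is completed before or after the cue.

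**The concern.** A score can measure cue-induced craving only if a cue came before it. Under the two schedules as written, the week 1 and week 3 AUQs follow no described cue but are labelled cue-induced. If the wording about week 2 or week 4 means a single follow-up session, the AUQ at the other of those two weeks is uncued as well.

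If all these scores enter one repeated-measures model, the treatment effect on the AUQ is a mixture of the effect on urge after a cue and the effect on background urge. The mixing proportions depend on length of stay and on when the session is held. That blurs the contrast between cue-induced and non-cued craving on which H1 is built, and an effect specific to cue reactivity may be diluted. The stated purpose of this pilot is to obtain unbiased effect sizes (Sample Size and Power), so an AUQ effect size of undefined construct is a real loss even though no power is claimed.

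**Working it through.** The plan gives no figure to reproduce: there is no power calculation, effect size or SD. The check sets the two schedules side by side and then asks how much dilution could follow.

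**Step 1. Count cued and uncued scores.** Inputs: AUQ weeks from Table 2; cue weeks and the 2-to-4-week stay from Design and methods; 10 participants, assumed complete. A stay of w weeks gives w + 1 AUQ scores.

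| Stay | Cue sessions | AUQ scores | Cued | Uncued | Uncued, 10 participants |
|---|---|---|---|---|---|
| 2 weeks | baseline, week 2 | 3 | 2 | 1 | 10 of 30 |
| 3 weeks | baseline, week 2 | 4 | 2 | 2 | 20 of 40 |
| 3 weeks | baseline only | 4 | 1 | 3 | 30 of 40 |
| 4 weeks | baseline and one of weeks 2 and 4 | 5 | 2 | 3 | 30 of 50 |
| 4 weeks | baseline, weeks 2 and 4 | 5 | 3 | 2 | 20 of 50 |

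Weeks 1 and 3 are uncued under every reading.

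**Step 2. Dilution in the mean post-baseline difference.** Let the effect at cued visits be constant and equal to 1, and let the effect at uncued visits be f. The documents do not give f; the values 0, 0.5 and 1 are assumptions that span the range.

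- 4-week stay, one follow-up cue: (1 + 3f)/4 = 25%, 62.5%, 100%.
- 2-week stay: (1 + f)/2 = 50%, 75%, 100%.
- 4-week stay, cues at weeks 2 and 4: (2 + 2f)/4 = 50%, 75%, 100%.

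**Step 3. Dilution in a slope contrast.** For visits 0 to 4, the least-squares slope weight at week t is (t − 2)/10. Suppose the cued effect grows linearly by 0.25 a week and reaches 1 at week 4, and the uncued effect is f times that. The slope is multiplied by 4 to express it at week 4.

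- Follow-up cue at week 4: 4 × [−0.25f + 0.75f + 2]/10 = 0.8 + 0.2f, that is 80%, 90%, 100%.
- Follow-up cue at week 2 only: 4 × [−0.25f + 0.75f + 2f]/10 = f, that is 0%, 50%, 100%. Week 2 is the midpoint and has zero weight in the slope.

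The answer therefore depends on f, on session timing and on the form of the contrast. The plan fixes none of these.

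**Step 4. Does a fall from cued to uncued scores bias the comparison?** Suppose uncued scores are lower by C in both arms. The post-baseline mean falls by C/2 for a 2-week stay and by 3C/4 for a 4-week stay with one follow-up session. If stays are balanced, this cancels between arms. If one arm of 5 has two more 4-week stays than the other, with the remaining stays 2 weeks, the contrast shifts by (2/5) × (3C/4 − C/2) = 0.1C.

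**The case against.** The strongest reply is that the plan never says the scores are pooled. Statistical Analysis does not list the AUQ visits in the model, and the weekly-summary sentence concerns description, not the hypothesis test. Cues may in fact be given weekly, in which case the Design and methods sentence is the one in error and every AUQ is cued. This stands in part: pooling is the plain reading of a weekly AUQ and an unrestricted repeated-measures model, but it is an inference. The two schedules conflict in either case.

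Three stronger readings are tempting and not supported.

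- A reader might infer that the standardised effect is halved or quartered. That needs no drug effect at all at uncued visits, whereas H1 predicts a decrease in non-cued craving too. Averaging also shrinks the SD: with equal SDs and a within-person correlation of 0.5 (an assumption), the mean of four scores has SD factor √(2.5/4) = 0.79, so 0.25 becomes 0.25/0.79 = 0.32.
- A reader might infer that the drop from a cued baseline to an uncued week 1 biases the treatment comparison. A fall common to both arms largely cancels; only imbalance in length of stay leaves a remainder (step 4).
- A reader might infer from Table 2 that only one AUQ is given per visit, so that no pre-cue score exists. The table marks visits, not administrations within a visit. A between-arm comparison of post-cue urge is in any case a legitimate randomised contrast.

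It is also fair to say that this is a 10-patient pilot and that the other craving measure, the PACS, is untouched.

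**Conclusion.** The point holds as an unreconciled schedule combined with an unspecified set of analysed visits. As written, between one third (10 of 30) and three fifths (30 of 50) of the AUQ scores labelled cue-induced follow no described cue, for complete participants who stay 2 or 4 weeks. The plain reading of the model combines them with cued scores, in one of the two parts of the primary goal.

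The direction of concern is dilution of an effect specific to cue reactivity. Its size is not determined by the documents: the retained share runs from 25% to 100% for the mean contrast in a 4-week stay with one follow-up cue at week 4, and from 80% to 100% for the slope contrast in the same setting under a linearly growing effect. These figures rest on assumed values of f and complete data. No single dilution factor should be quoted.

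**What to change.** 1. Reconcile Design and methods with Table 2. State at which visits cues are given, whether week 2 or week 4 means one session or both, and that the cue-induced AUQ is completed directly after the cue. If cues are really weekly, correct the Design and methods sentence.
2. Count only AUQs from cue sessions as the cue-induced outcome. Alternatively, keep all AUQs and add a cued/uncued term and its interaction with treatment to the hierarchical model. Label the remaining weekly AUQs as uncued urge in Table 2 and in the weekly summaries.
3. Preferably, base the main comparison on one post-baseline cue session common to all participants. The end of week 2 is already an option in the protocol and fits every planned stay. Use the baseline cued AUQ as covariate.
4. Do not adjust for a pre-cue AUQ taken at follow-up. It is measured after randomisation, H1 expects treatment to change it, and conditioning on it would remove any effect that acts through background craving.

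The cost is a table edit and a few sentences, plus a cue flag per visit, which needs no new data if session dates are recorded. The downside is fewer scores for the cue-induced endpoint: two per participant (three if cues are given at both weeks 2 and 4) instead of three to five, so 20 (or 30) instead of 30 to 50 for 10 complete participants.

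### The AUQ is scheduled once per time point and is not tied to the virtual-reality cue sessions, so the plan can show neither how much urge the cues provoke nor that it settles afterwards, including at a last session that may fall near discharge

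*Combined protocol and SAP*

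**What the plan says.** Design and methods has every participant "exposed to alcohol-related cues using virtual reality technology at baseline, at the end of week 2 or end of week 4". The same section puts the average hospital stay at 2 to 4 weeks and sets the length of follow-up from it: "the study period will last 2 to 4 weeks depending on" how long the patient remains. Ten patients are planned.

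Aims and hypothesis makes cue-induced and non-cued craving the primary goal. Assessment and Outcomes Measures assigns the AUQ to the cue-induced part and the Penn Alcohol Craving Scale (PACS) to the non-cued part. Table 2 marks both once at baseline and once in each of weeks 1 to 4. In Table 1, actigraphy is the only measure marked at discharge.

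The Safety paragraph reads: "Safety assessments will be collected weekly throughout the study". On content it adds: "These assessments will consist of monitoring and recording of adverse events and periodic measurement of vital signs". Craving is not part of it, and the cue sessions are not mentioned.

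The Background gives the context. It cites animal work in which orexin antagonists reduced, among other things, "reinstatement of alcohol use induced by cues and stress". On patients with alcohol use disorder it says that "insomnia is a common problem that is associated with alcohol craving and relapse".

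**The concern.** The cue session is a study procedure designed to raise alcohol urge in inpatients with alcohol use disorder. Two things depend on measuring its effect properly.

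The first is the outcome. H1 predicts a greater fall in cue-induced craving with lemborexant. If the AUQ is taken once, with no stated position relative to the cues, a lower score may mean that the cues provoke less urge, or only that the patient arrived with less. These are different drug effects, and the plan has a separate scale for the non-cued kind.

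The second is safety. The plan has no reading that would show urge returning to its pre-session level, and no adverse-event enquiry attached to the session. For some patients the final session may come close to the end of the stay, and no contact after discharge is described.

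**Working it through.** The plan states no figure to reproduce. The check sets the schedules side by side and works out the timing.

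**1. Cue sessions against AUQ marks**

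| Time point | Cue session (Design and methods) | AUQ marks (Table 2) |
|---|---|---|
| Baseline | yes | 1 |
| Week 1 | none listed | 1 |
| Week 2 | yes, subject to the *or* | 1 |
| Week 3 | none listed | 1 |
| Week 4 | yes, subject to the *or* | 1 |

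At least 2 of the 5 marks labelled cue-induced (weeks 1 and 3) have no listed cue exposure. If the *or* means one follow-up session per patient, a 4-week patient has 2 sessions and 5 marks, so 5 − 2 = 3 marks have no session. No time point has more than one mark.

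**2. What one score can show**

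Write the AUQ after cues as S = U + C, where U is the urge present before the cues and C is the rise they provoke. The change from baseline is then ΔS = ΔU + ΔC, and the difference between arms in ΔS is the sum of the differences in ΔU and ΔC. One reading per session gives S only, so the two parts cannot be separated. The PACS does not supply U, because it is a different scale, not timed to the session, and cannot be subtracted from the AUQ. With a reading just before the cues, post minus pre gives C directly. With a further reading after recovery, recovery minus pre shows whether the rise has gone.

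**3. Inpatient time after the last session**

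Assumption: study weeks count from admission. Let L be the stay in days.

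- L = 14, week-2 session: 14 − 14 = 0 days.
- L between 14 and 28, last listed session at week 2: gap = L − 14. For L = 21 this is 7 days; the range runs from just above 0 to just under 14.
- L = 28, week-4 session: 28 − 28 = 0 days.

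If baseline falls d days after admission, the gap after a given session shortens by d days, and a patient at the exact end of the range may leave before the scheduled session.

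**4. Monitoring around the sessions**

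With one follow-up session each there are 10 × 2 = 20 sessions. If every patient stayed 4 weeks and had both follow-up sessions there would be 10 × 3 = 30. None has a stated pre-cue reading, recovery reading or session-linked adverse-event enquiry. The 10 baseline sessions are followed by further weekly safety collection and the week-1 AUQ and PACS. After a last session at the very end of the stay, no later weekly assessment remains, and the plan does not say whether the final one comes before or after the session.

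**The case against.** The strongest reply is that the documents never place a session on or near the day of discharge. They give an average stay, not a distribution, and coincidence with discharge follows only for stays of about 2 or 4 weeks. This is correct. A reader might infer that all 10 patients are cued and then leave at once; the text does not support that.

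Four other stronger readings also fail.

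- *That the protocol itself ties craving to relapse.* The Background links insomnia to both, and its evidence on cues and return to drinking comes from animals. Nothing in the documents shows that a cue session increases drinking after discharge.
- *That patients are unmonitored.* Adverse events are collected weekly, nursing staff are present, and inpatient therapy continues. The accurate statement is that none of this is linked to the sessions.
- *That the cue session is the only risk the study adds.* Lemborexant is also assigned by the study.
- *That patients are rated at peak urge.* The plan does not say when the AUQ is given relative to the cues.

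It can also be said that measurement and safety are separate questions, and that a consent form or site procedure may describe a debrief. Both remarks are fair. Consent material was not part of the text examined, so the finding concerns what the protocol and SAP specify. The two questions are treated together here because the same added readings answer both. None of these replies supplies a pre-cue or recovery reading.

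**Conclusion.** The point holds in a limited form. As written, the plan cannot separate cue-provoked urge from urge already present, and cannot show that provoked urge has settled. This applies to every cue session, 20 or up to 30 depending on how the *or* is read, and it affects part of the primary goal. The mismatch between Table 2 and Design and methods at weeks 1 and 3 is plain from the text.

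The closeness of the last session to discharge is an inference. It rests on weeks being counted from admission and on a stay of about 2 or 4 weeks. For stays in between, the gap may reach just under 14 days. How many of the 10 patients would be affected cannot be determined. The conclusion does not depend on alpha, effect size or dropout.

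**What to change.** - At each cue session, give the AUQ immediately before the cues, immediately after, and again after a short recovery. Show the three readings in Table 2.
- In Statistical Analysis, define cue-induced craving as the pre-to-post change, or as the post-cue score adjusted for the pre-cue score, and name one of the two in advance. AUQ scores from weeks without cues should not enter that outcome.
- Add to the Safety paragraph an adverse-event enquiry recorded after each session.
- Reconcile Design and methods with Table 2 on which weeks have cue exposure, and say whether a 4-week patient has one or two follow-up sessions.
- State when the last session falls relative to discharge. Any action threshold or rule on discharge timing is for the sponsor and the treating team, and none is proposed here.

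The cost is two extra short ratings per session on an instrument already in use: 2 × 20 = 40 ratings across the study, or at most 2 × 30 = 60, with slightly longer sessions.

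### AUQ readings in weeks with no stated virtual-reality cue are labelled cue-induced, so the first primary craving outcome, on its natural reading, mixes cued and uncued urge

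*Combined protocol and SAP*

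**What the plan says.** The primary goal in Aims and hypothesis is the effect of augmentation "on cue-induced and non-cued alcohol craving scores". H1 predicts that the lemborexant group "will have a greater decrease in cue-induced and non-cued alcohol craving scores than naltrexone plus placebo". The two kinds of craving are named separately and each has its own instrument: "Cue-induced alcohol cravings will be assessed using the Alcohol Urge Questionnaire (AUQ", with the PACS for non-cued craving.

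On cue exposure, Design and methods says: "All participants will be exposed to alcohol-related cues using virtual reality technology at baseline, at the end of week 2 or end of week 4". No other exposure is described. On follow-up, the same section says "the study period will last 2 to 4 weeks depending on the patient's length of stay".

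Table 2 has the row "Cue-induced alcohol craving Alcohol Urge Questionnaire (AUQ) X x x x x", whose columns are baseline and weeks 1, 2, 3 and 4.

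Statistical Analysis asks for weekly summaries of every outcome and for a hierarchical linear model that allows for "correlation of repeated measurements (level 1) within participants (level 2". It names no set of AUQ visits, no time term, no contrast and no term for cue status.

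**The concern.** The protocol makes the presence of a cue the feature that separates one primary craving outcome from the other. An AUQ taken without a cue does not measure what its row in Table 2 says it measures. Weeks 1 and 3 have an AUQ but no stated cue. If a patient has only one later session, week 2 or week 4 has none either.

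If all these readings enter one model as a single outcome, that outcome changes meaning from visit to visit, and cue status is tied to time and to length of stay. Sample Size and Power gives unbiased effect sizes as the purpose of the pilot. An estimate that mixes cue states would not be the effect size for cue-induced craving, and a later trial planned on it would inherit the problem.

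**Working it through.** The plan states no effect size, standard deviation or power, so there is no figure to reproduce. The check is a count followed by simple algebra.

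**Inputs from the document.** Cue sessions, length of stay and 10 patients split equally, so 5 per arm (Design and methods); AUQ visits (Table 2).

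**Assumptions not in the document.** r = drug effect on uncued AUQ divided by drug effect on cued AUQ. D = rise in AUQ produced by the cue, equal in both arms. An AUQ at a session visit counts as cued, although its timing relative to the session is not given.

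**Step 1: count the readings.**

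| Stay and later session(s) | AUQ readings | No stated cue | Cued share s after baseline |
|---|---|---|---|
| 2 weeks, week 2 | 3 | 1 (week 1) | 1/2 |
| 4 weeks, week 4 only | 5 | 3 (weeks 1, 2, 3) | 1/4 |
| 4 weeks, week 2 only | 5 | 3 (weeks 1, 3, 4) | 1/4 |
| 4 weeks, weeks 2 and 4 | 5 | 2 (weeks 1, 3) | 2/4 |

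No session rule is given for a 3-week stay. With a session at week 2 (assumption), 2 of 4 readings have no cue and s = 1/3, which lies between the rows above.

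**Step 2: average post-baseline contrast.** Share of the cued effect kept = s + (1 − s)r.

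| s | r = 0 | r = 0.5 | r = 1 | r = 1.25 |
|---|---|---|---|---|
| 0.50 | 0.50 | 0.75 | 1.00 | 1.125 |
| 0.25 | 0.25 | 0.625 | 1.00 | 1.1875 |

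**Step 3: slope contrast.** Let the drug effect grow linearly from zero at baseline, and compare the least-squares slope with the slope if every reading were cued. For 4 weeks with a session at week 2 only and r = 0.5, the effects are (0, 0.5, 2, 1.5, 2) and the centred times (−2, −1, 0, 1, 2). The ratio is (−0.5 + 0 + 1.5 + 4)/10 = 0.50. In the order of the table in step 1, the ratios are:

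- r = 0.5: 1.00, 0.90, 0.50, 0.90
- r = 0: 1.00, 0.80, 0.00, 0.80
- r = 1: 1.00 throughout

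The 2-week ratio is always 1.00 because week 1 has zero weight in a slope through weeks 0, 1 and 2.

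**Step 4: change with no drug effect.** Baseline is cued, so the mean post-baseline change is −(1 − s)D: −0.50D for s = 1/2 and −0.75D for s = 1/4. This occurs in both arms. Now suppose each patient has one later session, at week 2 in a 2-week stay and week 4 in a 4-week stay. Let one arm have four 2-week stays and one 4-week stay, and the other arm the reverse:

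- first arm: (4 × −0.50D + 1 × −0.75D)/5 = −0.55D
- second arm: (1 × −0.50D + 4 × −0.75D)/5 = −0.70D
- spurious difference: 0.15D

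If 4-week patients have both later sessions, s = 1/2 for everyone and this difference is zero.

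**The case against.** A reader might infer that the plan has decided to pool cued and uncued readings and that the primary effect is therefore diluted. Neither is established.

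- **Pooling.** Statistical Analysis does not list the AUQ visits in the model, and restricting the analysis to session visits would also fit its wording. Pooling is the natural reading of that section together with Table 2, but it is an inference.
- **Dilution.** For an average contrast this needs r below 1. The document gives no r, and H1 predicts benefit on both kinds of craving. At r = 1 nothing is lost, and above 1 the effect is inflated. H1 speaks of a decrease, for which a slope is a reasonable contrast, and step 3 shows that a slope can keep most or all of the cued effect.
- **Shared fall.** A fall common to both arms cancels in expectation from the randomised comparison. It misleads within-arm description, and reaches the arm difference only through chance imbalance in length of stay.
- **Incomplete schedule.** The sentence on cue exposure is loosely worded. A cue may in fact be intended with every weekly AUQ, and the document cannot settle this.
- **Scale.** This is a 10-patient pilot, and cue status could be rebuilt from session dates if those are kept.

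The first three limit what can be claimed about bias. The fourth does not remove the point: if every AUQ is cued, Design and methods is wrong; if not, the Table 2 label is. The fifth makes the correction cheap rather than unnecessary.

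**Conclusion.** The point holds as a conflict over what a primary outcome measures, left unresolved by the analysis section. On the stated cue schedule, between 1 of 3 and 3 of 5 AUQ readings per patient in 2- and 4-week stays carry the cue-induced label with no stated cue. If they enter the model as the plan most naturally reads, the estimate cannot be interpreted as an effect on cue-induced craving.

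The document does not support a statement that the effect is diluted. Under an average post-baseline contrast the share kept is 25% to 50% at r = 0, 62.5% to 75% at r = 0.5, 100% at r = 1, and above 100% for larger r. Slope contrasts vary with the visit pattern. The 0.15D difference is an illustration that depends on a 4-versus-1 split of stays and one later session each. These figures rest on r and D, for which the document gives no value.

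**What to change.** 1. Reconcile Design and methods with Table 2: state which visits include a virtual-reality session, whether a 4-week patient has one later session or two, and what applies to a 3-week stay.
2. Record with every AUQ whether a cue was shown (yes/no).
3. In Statistical Analysis, define the cue-induced outcome as AUQ readings taken in a virtual-reality session, and analyse the other AUQ readings as a separate uncued-urge outcome. Alternatively, keep all readings in one model with cue-status and arm-by-cue-status terms, and take the primary contrast at cued visits.

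With session readings only, s = 1 and the share of the cued effect kept is 1.00 whatever r is.

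The cost is wording, one field per AUQ, and fewer readings for this outcome: one post-baseline reading per patient, or two if both later sessions are held, instead of two to four. As an indication, assume a correlation of 0.5 between readings. The mean of m readings has relative standard error √((1 + (m − 1) × 0.5)/m), which is 1 for m = 1, 0.866 for m = 2 and 0.791 for m = 4. Using session readings only then raises the standard error by about 15% (one reading instead of two), 26% (one instead of four) or 10% (two instead of four).
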